11. APPENDIX B: TARGETED AUDIENCE (PROLIFIC WEBSITE)

1. Age

- 18 years old or above

2. Current country of residence

- UK

3. Fluent language

- English

4. Diet restriction

- None

5. Gender

50% of participants

- Male

50% of participants

- Female

6. Students

96.5% of participants

- No

3.5% of participants

- Yes

7. Highest education level completed

50% of participants

- No formal qualifications
- Secondary education (e.g. GED/GCSE)
- High school diploma/A-levels

50% of participants

- Technical/community college
- Undergraduate degree (BA/BSc/other)
- Graduate degree (MA/MSc/MPhil/other)
- Doctorate degree (PhD/other)

12. APPENDIX C: RECRUITMENT TEXT

"This is a study examining eating behaviour. You will be asked to choose how much of several dishes you would serve yourself if you were eating it as a main meal and to fill some questionnaires in about yourself.

Overall, the study will take about 25 minutes.

If you would like to take part, please make sure that:

- You have 25 minutes to complete this study, it must be taken in one sitting and you cannot exit and return to the study.*
- You read the instructions carefully and answer the questions as accurately as possible.*
- You agree to install a plugin to run the tasks. Instructions will be provided for how to install and uninstall the plugin.*

Failure to comply with these instructions may result in your submission being rejected. Attention checks have been included, failing them will result in your submission being rejected."

15. APPENDIX F: REQUIREMENTS

1. *Are you a fluent English speaker?*

- Yes
- No

If answer “No”, participant cannot take part of the study

2. *Do you currently reside in the UK?*

- Yes
- No

If answer “No”, participant cannot take part of the study

3. *Do you have any dietary restriction?*

- None
- Vegetarian
- Vegan
- Gluten-free
- Sugar-free
- Diary/lactose-free
- Food allergy (e.g. milk, eggs, nut, wheat, fish, etc.)
- Other dietary restriction

If answer other than “None”, participant cannot take part of the study

If the participant cannot take part in the study, the following message will appear on the screen:

“Sorry, you are ineligible to take part in this study.

Please, go back to your Prolific page, return your submission and update your personal information.”

16. APPENDIX G: BASELINE QUESTIONNAIRE

1. *Gender*

- Male
- Female
- Other

2. *Age*

- __ (free text; range of 18-99)

3. *Ethnicity*

- White
- Black
- Asian
- Mixed
- Other

4. *What is your current employment status?*

- Full or part-time
- Student
- Retired
- Temporary or permanently sick or disabled
- Looking after home/family
- Other unemployed

5. *What is your highest educational qualification? If you are a student please select the diploma being studied for.*

- No qualification
- 1-3 GCSEs
- 4+ GCSEs
- A level
- CertHE
- DipHE
- Higher education or Bachelor's degree
- Post-Graduate degree
- Doctoral or professional degree

6. *After leaving school (i.e. at 16 years old), how many further years of higher education (i.e. a formal course) did you study for?*

Examples:

If you left school and did not go on to study further in higher education, your answer would be 0.

If you left school and then studied for two years for A levels, your answer would be 2.

If you completed A levels over two years and then also studied for a three-year undergraduate degree, your answer would be 5.

- __ (free text)

7. *What is your annual household income (after tax), including all earners in your household, in GBP (to the nearest £1000)?*

[figure not shown]
£_____ (free text; range 0-999,999)

8. How many adult(s) or child(ren) aged 14 and over live at your house, including you?
__ (free text; range of 1-20)

9. How many child(ren) aged under 14 live at your house, including you?
__ (free text; range of 1-20)

10. This is an attention check. How many times have you visited the planet Mars?
 Several times
 Just once
 Never

11. Think of a ladder (see the image below) as representing where people stand in society. At the top of the ladder are the people who are best off—those who have the most money, most education and the best jobs. At the bottom are the people who are worst off—who have the least money, least education and the worst jobs or no job. The higher up you are on this ladder, the closer you are to people at the very top and the lower you are, the closer you are to the bottom. Where would you place yourself on the ladder?

Choose the number whose position best represents where you would be on this ladder:

1 2 3 4 5 6 7 8 9 10

12. Are you currently dieting?
 Yes
 No

13. Weight

Select the unit:

- kg
- st and lb

— — —

14. Height

Select the unit:

- cm
- ft and in

— — —

15. *How hungry do you feel?*

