4. PARTICIPANTS AND RECRUITMENT

4.1. Recruitment

Participants will be recruited through Prolific, an online recruitment platform in which participants are compensated proportionate to the time it takes to complete the online study ($\approx 5\text{£}/\text{hour}$ reward participants). Participants' recruitment will be stratified by gender (50% male, 50% female), student status (3.5% yes and 96.5% no) [18] and qualification levels (50% A level or below, 50% above A level) in order to recruit participants of lower and higher SEP.

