7.2. Missing data

We do not anticipate missing data on the primary outcome and dependant variables because the online study will not allow missing answers. Data from participants who start but not finish the study will not be analysed. Submissions of participants who fail the attention checks or do not pass eligibility criteria will not be analysed. Any *a posteriori* withdrawal will be reported and reasons for withdrawal will be documented (e.g. incorrect answers, technical problems).

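### The education question behind the main SEP variable has no technical or vocational answer, although technical-college participants are recruited into the higher half

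*Combined protocol and SAP*

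**What the plan says.** Section 4.1 stratifies recruitment by "qualification levels (50% A level or below, 50% above A level"). Appendix B item 7 puts this into practice with a platform screener on "Highest education level completed". It places "Technical/community college" in the same half as undergraduate, graduate and doctorate degrees.

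The analysis does not use the screener. Section 7.1 builds the education variable from the survey answer, codes it 1 to 9, and cuts it into lower (codes 1–4, up to A level) and higher (codes 5–9, CertHE and above). Section 7.5 makes this binary variable the SEP measure in the main model. The survey question is Appendix G item 5: "What is your highest educational qualification? If you are a student please select the diploma being studied for". Its nine options run from no qualification through GCSEs, A level, CertHE and DipHE to degrees. None is technical, vocational or other, although the gender and ethnicity items on the same form do offer Other. Section 7.2 says that "the online study will not allow missing answers".

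Appendix M item 7 repeats the question with the same options as a consistency check. No section maps screener categories to survey codes or says what happens when the two disagree.

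**The concern.** A participant whose highest award came from a technical college enters through the higher quota and then meets a compulsory list that does not name that award. The nearest options lie on either side of the analysis cut: A level is code 4, and CertHE and DipHE are codes 5 and 6. A misfit here can therefore move a person across the cut.

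The consistency check asks the same question with the same options. It catches careless answering, but not a participant who makes the same wrong choice twice.

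A stronger effect in higher SEP is one of the primary hypotheses in Section 2, and it is tested by the label by education interaction. A significant interaction also opens the stratified models (Section 7.5) and the moderated mediation (Section 7.7). Item 5 is answered before the meal task (Section 6), so errors should not depend on the label seen. The expected consequence is a smaller interaction and lower power for it.

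**Working it through.** **Inputs.** From Section 7.9: 1,600 analysed, alpha 0.05, interaction f = 0.07, stated power 0.80. From Section 4.1: a 50/50 education quota, so 800 and 800, and "student status (3.5% yes and 96.5% no"). The share of technical-college recruits and the way they would answer item 5 are not in the documents. Assumed: 5–20% of the higher quota, with half to all answering A level or below. The calculation treats the screener class as true.

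**Step 1: the plan's own figure.** The non-centrality is f² × N = 0.0049 × 1,600 = 7.84. With eight cells and one numerator degree of freedom, the non-central F gives power 0.799, which reproduces 0.80. A hand check: √7.84 = 2.80, and 2.80 − 1.96 = 0.84, which corresponds to 0.80. The full four-by-two interaction in Section 7.5 has three degrees of freedom and gives 0.643 at the same f. That is a separate matter. The one-degree version is used below because it is the one that matches the plan.

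**Step 2: shrinkage.** If t people move from the higher quota to the analysed lower group, the analysed groups are 800 − t and 800 + t. The contrast keeps the fraction 1 − t/(800 + t). Imbalance multiplies this by √(4 × n_H × n_L)/1,600. The effective f is 0.07 times the product.

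| College share of higher quota | Share answering A level or below | t | Analysed higher / lower | Contrast kept | After imbalance | Effective f | Power (1 df) |
|---|---|---|---|---|---|---|---|
| none | – | 0 | 800 / 800 | 1.000 | 1.000 | 0.0700 | 0.80 |
| 5% | half | 20 | 780 / 820 | 0.976 | 0.975 | 0.0683 | 0.78 |
| 5% or 10% | all or half | 40 | 760 / 840 | 0.952 | 0.951 | 0.0666 | 0.76 |
| 10% or 20% | all or half | 80 | 720 / 880 | 0.909 | 0.905 | 0.0633 | 0.72 |
| 20% | all | 160 | 640 / 960 | 0.833 | 0.816 | 0.0572 | 0.63 |

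Last row in full: 1 − 160/960 = 0.833; √(4 × 640 × 960)/1,600 = 0.980; 0.833 × 0.980 = 0.816; 0.07 × 0.816 = 0.0572.

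**Step 3: imbalance alone.** If the survey answer is taken as the true class, nobody is misplaced and only the split changes. At 640/960 the factor is 0.980 and power is about 0.78.

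**Step 4: students.** They number at most 0.035 × 1,600 = 56. The extreme case is that all sit in the lower quota and study above A level: 56/856 = 6.5% of the analysed higher group, contrast 0.935, power 0.74. If they split evenly between the quotas and the lower-quota half all study above A level, 28 move: 28/828 = 3.4%, contrast 0.966, power 0.77. Both figures again treat the screener as true.

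**The case against.** The best defence is that a disagreement between screener and survey is not in itself an error in the analysed variable. The nominal cut is the same in Section 4.1, Section 7.1 and Appendix B. The screener is a recruitment tool, and the plan deliberately asks education again in finer categories and analyses that answer. CertHE and DipHE are sub-degree options coded higher, so some college recruits have a plausible answer on the side they were recruited into. Others may answer A level truthfully and be placed correctly. The documents give neither their number nor the level of their awards. All of this stands, and it limits what can be said about size. It does not remove the gap, which lies inside the survey question: a respondent whose award is not listed has no accurate answer, whatever the screener recorded.

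A reader might infer that the student instruction is a second error, since "If you are a student please select the diploma being studied for" departs from a screener on completed education. The documents do not support that. The wording is the same in Appendices G and M and is an explicit choice of construct. It is capped by the 3.5% quota. Students who already hold a higher qualification, or who study for A level or below, do not cross the cut. Asking for completed education instead would be a trade-off, not a correction.

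The plan also has partial protection. Section 7.6 substitutes a composite education score, but that score still contains item 5. Section 7.7 repeats the analysis with income and subjective status. These do not depend on item 5, but they are different constructs and are tested at 0.01.

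**Conclusion.** The gap is real and worth closing: a compulsory question that defines the main SEP variable has no answer for a group that the plan expressly recruits, and its only check cannot show the resulting error. The expected direction is a smaller label by education interaction.

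The size is not established. The fall in one-degree power from 0.80 to about 0.78–0.63 rests on an assumed college share of 5–20% of the higher quota, on half to all of these answering A level or below, on the screener class being true, and on errors unrelated to arm. It shows what could happen and is not an estimate.

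Three stronger readings are not supported. Recruitment and analysis do not use different cut points; the question and the student rule differ, but the A level cut does not. A departure from 50/50 is not costly in itself, since power stays near 0.78 even at 640/960. The overall comparison of labels is not biased, because labels are randomised and education plays no part in allocation.

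**What to change.** In Appendix G item 5 and Appendix M item 7, add two technical/vocational answers: one for awards equivalent to A level or below, and one for awards above A level. In Section 7.1, assign the first to lower and the second to higher, and give each a place in the 1–9 coding.

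In Section 7, add a cross-tabulation of screener class by survey class. Add a sensitivity analysis of the main model that excludes students and participants whose two classes disagree. State in Section 7.1 that students are classed by the qualification they are studying for, as a deliberate choice.

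The cost is two answer options in each item, a few lines of text, and keeping the screener class with the participant ID that the result files already hold. The one real downside is the 1–9 coding: each new option spans several existing levels, so its code in the composite score is a judgement to fix in advance. If the questionnaire can no longer change, the cross-tabulation and the sensitivity analysis can still be added.

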4.2. Inclusion criteria

- UK residents, age ≥ 18
- Fluent in English
- Have access to a computer and Internet

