4.3. Exclusion criteria

- Having any dietary restriction:
 - Vegetarian
 - Vegan

- Gluten-free
- Sugar-free
- Diary/lactose-free
- Food allergy (e.g. milk, eggs, nut, wheat, fish, etc.)

- Taking part more than once:
Prolific is designed to avoid the same participant to take the same survey twice (i.e., one participant cannot access the study link twice). Each participant recruited on Prolific has a unique ID. If for some reasons a participant takes the survey twice, we will delete the second submission from the dataset by checking the ID duplicates. For the same reason, to avoid one participant takes the survey twice with different accounts, we will delete the second submission from the dataset by checking the IP duplicates.
- Failing an attention check (**Appendix G, item 9; Appendix H, item 10; Appendix O, item 4**).
- Completing the main task too fast, i.e., less than 2 sec per dish = less than 36 sec in total, that will be interpreted as careless or insufficient effort responding [19], [20].

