5.2. Measures of socioeconomic position

Five measures of socioeconomic status will be included. Participants will be asked to report:

- their highest educational qualification;
- their number of years in higher education;
- their current employment status;
- their household income and their household composition;
- a subjective measure of their socioeconomic position using the MacArthur Scale of Subjective Social Status (SSS) [23].

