7.1. Variables description

Primary outcome

The main outcome variable is the **total self-served energy** (in kcal).

Other outcomes:

Derived from the debriefing questionnaire:

1. Kcal influence (item 1): whether kcal content influences the quantity of self-served food;
2. PACE influence (item 2): whether physical activity energy equivalent influences the quantity of self-served food.

Answers to each item will be coded as: 1 = Strongly disagree; 2 = Disagree; 3 = Slightly disagree; 4 = Neutral; 5 = Slightly agree; 6 = Agree; 7 = Strongly agree.

Independent variables

SEP

¹ These data are collected to inform a future study and will not be analysed as part of this study.

Highest educational qualification will be coded from 1 to 9: 1 = No formal qualifications; 2 = 1–3 GCSEs; 3 = 4+ GCSEs; 4 = A level; 5 = Certificate of higher education (CertHE); 6 = Diploma of higher education (DipHE); 7 = Bachelor; 8 = Master's degree; 9 = Doctorate, and as a binary variable as *lower* (values: 1, 2, 3, 4) or *higher* (values: 5, 6, 7, 8, 9).

Years in higher education, as a continuous variable.

Level of education (composite score): Assuming that highest educational qualification and years in higher education will be significantly correlated (tested using Pearson's r), we will z-score the two variables and create an average of the two to form a level of education composite score.

Equivalised household income: The OECD-modified equivalence scale will be used to adjust household income considering household size and composition [27]. Equivalised household income is calculated by dividing the after-tax household (including all the earner to the nearest £1000) by the sum of the equivalence value of all the household members (1 = first adult; 0.5 = additional adult or child >14 years old; 0.3 = child aged 0-13 years old).

Subjective SEP: The measure of the Subjective Social Status using the MacArthur Scale will be coded from 1 (lower SSS) to 10 (higher SSS).

Executive function measures

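### Appendix G item 9 cannot record zero children under 14 as printed; a false entry of 1 would lower equivalised income by 10.7% to 23.1% in households of one to four people aged 14 or over

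*Combined protocol and SAP*

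**What the plan says.** Section 5.2 lists "their household income and their household composition" among the measures of socioeconomic position. Appendix G collects them in three items:

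- Item 7, after-tax household income, printed as "free text; range 0-999,999".
- Item 8, the number of people aged 14 or over, counting the respondent, printed as "free text; range of 1-20".
- Item 9, "How many child(ren) aged under 14 live at your house, including you", with the same printed range as item 8.

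Section 7.1 divides income by the sum of the household's equivalence values: 1 for the first adult, 0.5 for each further older member, and "0.3 = child aged 0-13 years old". Section 4.2 admits only "UK residents, age ≥ 18".

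Equivalised income is then used twice. It is a baseline characteristic compared between education groups (section 7.3), and it is one of two alternative measures of socioeconomic position with which the main analyses are repeated at the 0.01 level (section 7.7).

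**The concern.** The closing words and the minimum of 1 are right for item 8, because the respondent always belongs to that count. Neither can be right for item 9. No participant is under 14, and a household with no young child has no true answer within the printed range. The documents give no 'none' option, skip rule or recode. Item 7 shows that a range starting at zero was printed where one was wanted.

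A false count can arise in two ways:

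- **(a)** The live form enforces the minimum, and a participant with no young child enters 1 to proceed.
- **(b)** A parent follows the wording and adds themselves, for example entering 2 for one child. This needs no enforced minimum.

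Each way adds a false 0.3 to the divisor and understates equivalised income. The percentage depends on household composition, so the error is not a common scale factor and can change the order of households.

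**Working it through.** The plan states no equivalised-income figure, so there is nothing to reproduce. The check applies the section 7.1 formula to the Appendix G items.

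**Formula.** Let n be the item 8 count and c the true number of children under 14. The true divisor is W = 1 + 0.5(n − 1) + 0.3c. An entry one too high makes it W + 0.3, so the relative error in equivalised income is W/(W + 0.3) − 1 = −0.3/(W + 0.3).

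| People aged 14+ | No child, 1 entered (a) | One child, 2 entered (b) | Two children, 3 entered (b) |
|---|---|---|---|
| 1 | 0.3/1.3 = 23.1% low | 0.3/1.6 = 18.8% low | 0.3/1.9 = 15.8% low |
| 2 | 0.3/1.8 = 16.7% low | 0.3/2.1 = 14.3% low | 0.3/2.4 = 12.5% low |
| 3 | 0.3/2.3 = 13.0% low | 0.3/2.6 = 11.5% low | 0.3/2.9 = 10.3% low |
| 4 | 0.3/2.8 = 10.7% low | 0.3/3.1 = 9.7% low | 0.3/3.4 = 8.8% low |

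**Example.** With an assumed income of £30,000 and no young child, one person moves from £30,000 to 30,000/1.3 = £23,077. Four people move from 30,000/2.5 = £12,000 to 30,000/2.8 = £10,714.

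**Reordering.** Take a one-person household on £25,000 and a two-adult household on £36,000 (assumed incomes, no young child in either). The true values are £25,000 and 36,000/1.5 = £24,000. With 1 entered by both, they become 25,000/1.3 = £19,231 and 36,000/1.8 = £20,000, and the order reverses.

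**Sample level, illustrative only.** The documents give no distribution of income or household type. A simulation of 400,000 households in each of 243 scenarios assumed:

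- log-income SD of 0.4, 0.6 or 0.8;
- 20%, 35% or 50% of households with a child under 14, and among those one, two or three children in 45/40/15%;
- one to four people aged 14+ in mixes of 25/50/15/10, 40/40/10/10 or 15/60/15/10%;
- 25%, 50% or 100% of households without a young child entering 1;
- 0%, 10% or 25% of the others adding themselves;
- an education effect of 0.3 on log income, with composition independent of income and education.

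Results:

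- Mean equivalised income is 2.5–4.7%, 4.9–8.8% or 9.9–17.1% too low when 25%, 50% or 100% of households without a young child enter 1.
- Correlation with the correct value is 0.972 to 0.995.
- The standardised difference between education groups changes by −0.6% to +9.4%.
- For the income-by-label interaction, take a participant-level F test with 3 degrees of freedom, N = 1,600 and alpha 0.01. Power of 80% on the correct variable needs noncentrality 15.51. Multiplying by the squared correlation leaves power of 76.9% to 79.5%. This assumes the label effect varies linearly with correct equivalised income.

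**The case against.** The strongest reply is that this is a copying slip in a printed appendix and shows nothing about the data. The appendices are not a close guide to the live form. Section 4.3 places the attention checks at "Appendix G, item 9; Appendix H, item 10; Appendix O, item 4", yet "This is an attention check. How many times have you visited the planet Mars" is printed as item 10 of Appendix G, a second check sits in Appendix I, and Appendix O is unnumbered debriefing text. The programmed form may well accept zero. This stands, and it is why the income error is stated only conditionally. But the appendix is the only specification of the item, and the numbering mismatch is itself a reason to check the form against it.

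Second, the reach is small. The primary model uses binary education (section 7.5), so the primary analysis, sample size and allocation are untouched. Subjective social status, the other alternative measure, is unaffected. Item 9 is asked before the meal task (section 6), so no spurious label effect is expected. All of this stands.

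Third, the simulated shares have no basis in the documents, and the 2.5% floor follows from assuming that at least 25% of households without a young child enter 1. That is correct: if nobody does and no parent adds themselves, the error is zero. Route (b) also requires an adult just counted at item 8 to count themselves again as a child, which few may do.

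Fourth, respondents might leave the item blank. Section 7.2 says the online study does not allow missing answers, but the sentence concerns the primary outcome and dependent variables, so it does not settle whether item 9 is compulsory. Blank entries were not modelled.

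**Conclusion.** The concern holds. The printed item is wrong with high confidence: it excludes the true answer for every household without a child under 14 and invites adults to count themselves as children. The size per affected household is exact given the section 7.1 weights: 23.1% to 10.7% too low for one to four people aged 14 or over with no young child, and 18.8% to 8.8% for a parent of one or two children who adds themselves. Whether any recorded value is affected depends on the live form and on how people respond, which the documents do not show. If the error occurs, the reported income level could be clearly wrong, while the planned tests would probably change little; that second statement rests on the simulation assumptions. This should be corrected, but it does not threaten the primary result.

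**What to change.** **Before launch.** Reword item 9 to ask how many children under 14 live in the household, delete 'including you', set the range to 0–20, and check the programmed form against the corrected text. The cost is one field minimum and two words, with no change to sample size or alpha.

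**If data were already collected.** Look first for zeros at item 9; any zero shows that the minimum was not enforced for that entry. If the minimum was 1, keep all participants and state that the count is unreliable. Report the baseline income row and the equivalised-income analyses both as entered and with entries of 1 recoded to 0, and say whether the conclusion differs. The cost is a second baseline row and a second run of the equivalised-income repeat, including any follow-up models and pairwise comparisons triggered under section 7.5.

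The recode is a sensitivity check and not a bound. A true one-child household set to zero is overstated by 0.3/1.0 = 30.0%, 0.3/1.5 = 20.0%, 0.3/2.0 = 15.0% or 0.3/2.5 = 12.0% with one to four people aged 14 or over, and counts of 2 or more inflated by the wording are not repaired. The two versions need not bracket the truth, which is the reason to correct the item before launch.
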